## 6.1 Study Calendar

Period/ Procedure	Pre- Screening	Screening 	Cycle 1			Cycle 2	Future Cycles 	Restaging or Off-Study Visit Survival Follow-up
Study Day/Visit Day*	-365 to -28	-28 (±3)	1 (±3)	10-12 (±3)	15 (±3)	1 (±3)	1 (±3)	9 weeks Post Start of Tx (±7)
Study Treatment/Drug Administration								
Pembrolizumab			200 mg q every 3 weeks; start on C1D1					
Vorinostat			400 mg once a day, 4 days on, 3 days off, weekly every cycle					
Tamoxifen			20 mg once a day continuously					
Administrative Procedures								
Prescreening ICF	X							
Informed consent		X						
Clinical Assessments								
Physical exam		X	X		X	X	X	
Vital signs		X	X		X	X	X	
Performance status		X	X		X	X	X	
Medical history		X						
Concomitant medications		X	X		X	X	X	
Toxicity Assessment 		X	X		X	X	X	X 
Drug Diaries 			X			X	X	
Documentation of Response		X					X	

 All screening procedures must be performed within 28 days unless otherwise indicated. Pre-study tests, History and Physical may be used for Day 1 tests if within 2 weeks

 Cycle delays up to 14 days for non-medical reason (e.g. holidays) are acceptable without notification of regulatory agencies

 Therapy delay for palliative radiation should be based on discussion with the study sponsor and the treating physician, every effort should be made not to hold therapy, patients, where vorinostat is being held for more than 4 weeks, may stay on study if there is felt to be a benefit

 Toxicity assessment must be performed until all treatment-related toxicities have been resolved or decreased to grade 1. Adverse events must be recorded up to 30 days after termination on study

 Drug diaries will be administered for vorinostat and tamoxifen (oral drugs) only on the first day of every cycle

Period/ Procedure	Pre- Screening	Screening 	Cycle 1			Cycle 2	Future Cycles 	Restaging or Off-Study Visit Survival Follow-up
Study Day/Visit Day*	-365 to -28	-28 (±3)	1 (±3)	10-12 (±3)	15 (±3)	1 (±3)	1 (±3)	9 weeks Post Start of Tx (±7)
Laboratory Assessments								
Hematology 		X	X		X	X	X	
Comprehensive Metabolic Panel 		X	X		X	X	X	
Thyroid Function 		X				X	X (odd cycles)	
Tumor Markers 		X	X			X	X	
Pregnancy test 		X					X	
Lymphocyte Subset		X or C1D1 		X 			X  (end of C3)	
PBMC 		X or C1D1 		X 			X  (end of C3)	
PK testing		X or C1D1		X			X (end of C3)	
Biomarker testing (prescreening)	X							
Imaging Procedures								
CT/MRI 		X					X	X
Tissue Collection/ Biopsy								
Tumor FNA/Biopsy 		X or C1D1					X (end of C3)	

 Including CBC with differential and platelet count

 Sodium, Potassium, Chloride, blood urea nitrogen, Creatinine, Non-fasting glucose, Calcium, ALT, AST, Alkaline Phosphatase, Albumin, Total Bilirubin, Total Protein

 Including FT4 and TSH, TSH only for patients on thyroid replacement therapy

 CEA, Ca15-3, Ca 125 (if clinically indicated)

 For women of childbearing potential, performed within 14 days of starting treatment. Pregnancy test will be repeated if clinically indicated

 Correlative studies: Pre-study within 14 days, and end of cycle 3 (preferably day 17-19 while on vorinostat) prior to cycle 4 day 1 pembrolizumab infusion

 On day 10-12 pre-dose

 Staging studies within 30 days prior to day of start, restaging after cycle 3 (week 9 ±1w), 6 (week 18±1w), then 9, 12, then every 6 cycles if clinically indicated. Partial and complete responses must be confirmed at least one month apart from the first documentation of objective response. Scans may be performed more frequently if clinically indicated

\*Note: Window for all study procedures is ±3 days except for scans which is ±7 days

## 6.2 Schedule of Procedures and Observations

### 6.2.1 Prescreening Period

- Prescreening ICF
- Laboratory Assessments
  - Biomarkers testing (1 tbsp. blood draw)

## 6.3 Participant Registration

A written, signed, informed consent form (ICF) and a Health Insurance Portability and Accountability Act (HIPAA) authorization must be obtained before any study-specific assessments are initiated. A copy of the signed ICF will be given to the subject, and a copy will be filed in the medical record. The original will be kept on file with the study records.

All participants consented to the study will be registered in OnCore®, the UCSF Helen Diller Family Comprehensive Cancer Center Clinical Trial Management System (CTMS). The system is password protected and meets HIPAA requirements.

### 6.3.1 Pretreatment Period

#### 6.3.1.1 Screening Assessments

The Screening procedures and assessments must be completed within 28 days of initiating study treatment.

- Clinical Assessments
  - Documentation of disease assessment (CT scan)
  - Physical examination
  - Vital signs
  - Performance status
  - Complete medical history
  - Concomitant medication review
  - Toxicity assessment
  - Documentation of response
- Laboratory Assessments
  - Hematology labs - CBC with differential and platelet count
  - Comprehensive Metabolic Panel
  - Thyroid function
  - PK testing (or at C1D1)
  - Tumor markers
  - Pregnancy test
  - Lymphocyte Subset (or at C1D1)
  - PBMC (or at C1D1)
- Imaging Procedures

- CT / MRI of breast
- Tumor Tissue Collection
  - Tumor FNA/biopsy (or at C1D1)

### **6.3.2 Treatment Period**

#### **6.3.2.1 Study Procedures, Cycle 1, Day 1**

- Study Treatment/Drug Administration
  - Pembrolizumab (200 mg q every 3 weeks)
  - Vorinostat (400 mg once a day, 4 days on, 3 days off, weekly every cycle)
  - Tamoxifen (20 mg once a day continuously)
- Clinical Assessments
  - Physical examination
  - Vital signs
  - Performance status
  - Concomitant medication review
  - Toxicity assessment
  - Drug diaries
- Laboratory Assessments
  - Hematology labs - CBC with differential and platelet count
  - Comprehensive Metabolic Panel
  - PK testing (if not conducted at screening)
  - Tumor markers
  - Lymphocyte Subset (if not conducted at screening)
  - PBMC (if not conducted at screening)
- Tumor Tissue Collection
  - Tumor FNA/biopsy (if not conducted at screening)

#### **6.3.2.2 Study Procedures Cycle 1, Day 10-12**

- Study Treatment/Drug Administration
  - Pembrolizumab (200 mg q every 3 weeks)
  - Vorinostat (400 mg once a day, 4 days on, 3 days off, weekly every cycle)
  - Tamoxifen (20 mg once a day continuously)
- Laboratory Assessments
  - PK testing
  - Lymphocyte Subset
  - PBMC

### 6.3.2.3 Study Procedures Cycle 1, Day 15

- Study Treatment/Drug Administration
  - Pembrolizumab (200 mg q every 3 weeks)
  - Vorinostat (400 mg once a day, 4 days on, 3 days off, weekly every cycle)
  - Tamoxifen (20 mg once a day continuously)
- Clinical Assessments
  - Physical examination
  - Vital signs
  - Performance status
  - Concomitant medication review
  - Toxicity assessment
- Laboratory Assessments
  - Hematology labs - CBC with differential and platelet count
  - Comprehensive Metabolic Panel

### 6.3.2.4 Study Procedures Cycle 2, Day 1

- Study Treatment/Drug Administration
  - Pembrolizumab (200 mg q every 3 weeks)
  - Vorinostat (400 mg once a day, 4 days on, 3 days off, weekly every cycle)
  - Tamoxifen (20 mg once a day continuously)
- Clinical Assessments
  - Physical examination
  - Vital signs
  - Performance status
  - Concomitant medication review
  - Toxicity assessment
  - Drug diaries
- Laboratory Assessments
  - Hematology labs - CBC with differential and platelet count
  - Comprehensive Metabolic Panel
  - Thyroid function
  - Tumor markers

### 6.3.2.5 Study Procedures Future Cycles

- Study Treatment/Drug Administration
  - Pembrolizumab (200 mg q every 3 weeks)
  - Vorinostat (400 mg once a day, 4 days on, 3 days off, weekly every cycle)
  - Tamoxifen (20 mg once a day continuously)

- Clinical Assessments
  - Physical examination
  - Vital signs
  - Performance status
  - Concomitant medication review
  - Toxicity assessment
  - Drug diaries
  - Documentation of response
- Laboratory Assessments
  - Hematology labs - CBC with differential and platelet count
  - Comprehensive Metabolic Panel
  - Thyroid function (odd cycles)
  - PK testing (end of C3)
  - Tumor markers
  - Pregnancy test
  - Lymphocyte Subset (end of C3)
  - PBMC (end of C3)
- Imaging Procedures
  - CT / MRI of breast
- Tumor Tissue Collection
  - Tumor FNA/biopsy (end of C3)

#### **6.3.2.6 Study Procedures Restaging or Off-Study Visit**

- Study Treatment/Drug Administration
  - Pembrolizumab (200 mg q every 3 weeks)
  - Vorinostat (400 mg once a day, 4 days on, 3 days off, weekly every cycle)
  - Tamoxifen (20 mg once a day continuously)
- Clinical Assessments
  - Toxicity assessment
- Imaging Procedures
  - CT / MRI of breast

#### **6.3.3 Survival Follow-up**

After completing the follow-up period, participants will be contacted by telephone every 12 weeks to assess for survival/anti-cancer therapy status until death, withdrawal of consent, or the end of the study, whichever occurs first.

## 6.4 Correlative Studies

### 6.4.1 Histone Acetylation in peripheral blood mononuclear cells

Exposure to HDAC inhibitors results in inhibition of histone deacetylation. Histone acetylation (mainly histone H3) has been used as a biological marker of HDAC inhibitor activity. H3 acetylation has been measured successfully in PBMCs in clinical trials using vorinostat and other HDAC inhibitors. We will, therefore, measure H3 and H4 acetylation in peripheral blood mononuclear cells and tumor samples of patients before and after treatment with vorinostat.

Mononuclear cells will be obtained prior to treatment initiation and repeated on day 10 (+2) and at the end of cycle 3 (day 17-19). Cells will be isolated from patient blood by centrifugation at 400 x g (Sorvall, HS4 rotor) for 30 min using a Ficoll-Paque gradient (Sigma, St. Louis, MO) as described by Sandor et al. Histone acetylation will be quantified by WB analysis of PBMCs using an acid extraction method to collect nuclear histone proteins.

### 6.4.2 Evaluation of vorinostat effects on tumor tissue acetylation and changes in estrogen receptor expression

Post-treatment tumor samples and PBMCs (as well as the vorinostat PK samples) will be obtained on cycle 3 (days 17-19) after the vorinostat morning dose. Fine needle aspirations (FNA) and core biopsies will be obtained either by an interventional radiologist (visceral disease, lymph node) or a cytopathologist (subcutaneous and skin lesions). Diff-Quick air-dry method (FNA) or touch prep analysis (core biopsies) at time of biopsy will be used to confirm the presence of tumor. Tumor samples will be divided and processed for specific techniques as listed below. An attempt for three cores will be made using the appropriate needle. Tissues will be evaluated for the effects of vorinostat on histone acetylation and estrogen expression (by IHC). For IHC, tumors will be fixed in formalin (1 hour/mm thickness), dehydrated, blocked in paraffin. Five-micron sections will be stained with the appropriate antibodies and visualized by light microscopy. Staining will be evaluated using Adobe Photoshop. As the tumor biopsies may contain a mixture of tumor and surrounding cells, cells will be stained (in addition to ER and H3) with specific antibodies used to distinguish tumor versus non-tumor tissues (e.g., cytokeratin (Keratin (5D3)) for breast cancers. PBMCs histone acetylation and ER expression will be quantified by Western blot.

### 6.4.3 Logistics on Immune modulation

For immune assays we will collect 60cc of blood in green top tubes at baseline and day 10-12 in cycle 1 and on day 17-18 in cycle 3, at the time points specified above for tumor biopsies, FFPE for immune cell infiltrate and a frozen section will be obtained for TCR sequencing.

## 6.5 Use of Concurrent/Concomitant Medications

### 6.5.1 Acceptable Concomitant Medications

All treatments that the investigator considers necessary for a subject's welfare may be administered at the discretion of the investigator in keeping with the community standards of medical care. All concomitant medication will be recorded on the case report form (CRF) including all prescription, over-the-counter (OTC), herbal supplements, and IV medications and fluids. If changes occur during the trial period, documentation of drug dosage, frequency, route, and date may also be included on the CRF.

All concomitant medications received within 28 days before the first dose of trial treatment and 30 days after the last dose of trial treatment should be recorded. Concomitant medications

administered after 30 days after the last dose of trial treatment should be recorded for SAEs and ECIs as defined in Section 7.3.

Anti-diarrheal and anti-emetic treatment may be given as required, either therapeutically or prophylactically, after such events have occurred in conjunction with a prior dose given without antidiarrheals or anti-emetics. If needed, efforts will be made to standardize such supportive regimens in agreement with participating Investigators.

Other examples of supportive care medications include prophylactic or therapeutic use of erythropoietin for anemia and bisphosphonates (e.g., pamidronate).

## 6.5.2 Rescue Medications & Supportive Care

### Supportive Care Guidelines

Subjects should receive appropriate supportive care measures as deemed necessary by the treating investigator, including but not limited to the items outlined below:

- Diarrhea: Subjects should be carefully monitored for signs and symptoms of enterocolitis (such as diarrhea, abdominal pain, blood or mucus in stool, with or without fever) and bowel perforation (such as peritoneal signs and ileus). In symptomatic subjects, infectious etiologies should be ruled out, and if symptoms are persistent and/or severe, endoscopic evaluation should be considered.
  - In subjects with severe enterocolitis (Grade 3), pembrolizumab will be permanently discontinued, and treatment with systemic corticosteroids should be initiated at a dose of 1 to 2 mg/kg/day of prednisone or equivalent. When symptoms improve to Grade 1 or less, corticosteroid taper should be started and continued over at least 1 month.
  - In subjects with moderate enterocolitis (Grade 2), pembrolizumab should be withheld, and anti-diarrheal treatment should be started. If symptoms are persistent for more than one week, systemic corticosteroids should be initiated (e.g., 0.5 mg/kg/day of prednisone or equivalent). When symptoms improve to Grade 1 or less, corticosteroid taper should be started and continued over at least 1 month. Regarding guidelines for continuing treatment with pembrolizumab, see Section 5.2.1.
  - All subjects who experience diarrhea should be advised to drink liberal quantities of clear fluids. If sufficient oral fluid intake is not feasible, fluid and electrolytes should be substituted via IV infusion.
- Nausea/vomiting: Nausea and vomiting should be treated aggressively, and consideration should be given in subsequent cycles to the administration of prophylactic antiemetic therapy according to standard institutional practice. Subjects should be strongly encouraged to maintain liberal oral fluid intake.
- Anti-infectives: Subjects with a documented infectious complication should receive oral or IV antibiotics or other anti-infective agents as considered appropriate by the treating investigator for a given infectious condition, according to standard institutional practice.
- Immune-related adverse events: Please see Section 5.2 below and the separate guidance document in the administrative binder regarding diagnosis and management of adverse experiences of a potential immunologic etiology.

- Management of Infusion Reactions: Acute infusion reactions (which can include cytokine release syndrome, angioedema, or anaphylaxis) are different from allergic/hypersensitive reactions, although some of the manifestations are common to both AEs. Signs and symptoms usually develop during or shortly after drug infusion and generally resolve completely within 24 hours of completion of infusion. Signs/symptoms may include: Allergic reaction/hypersensitivity (including drug fever); Arthralgia (joint pain); Bronchospasm; Cough; Dizziness; Dyspnea (shortness of breath); Fatigue (asthenia, lethargy, malaise); Headache; Hypertension; Hypotension; Myalgia (muscle pain); Nausea; Pruritis/itching; Rash/desquamation; Rigors/chills; Sweating (diaphoresis); Tachycardia; Tumor pain (onset or exacerbation of tumor pain due to treatment); Urticaria (hives, welts, wheals); Vomiting.

### Contraception

Pembrolizumab, tamoxifen, and vorinostat may have adverse effects on a fetus in utero. Furthermore, it is not known if pembrolizumab has transient adverse effects on the composition of sperm. Non-pregnant, non-breast-feeding women may be enrolled if they are willing to use 2 methods of birth control or are considered highly unlikely to conceive. Highly unlikely to conceive is defined as 1) surgically sterilized, or 2) postmenopausal (a woman who is  $\geq 45$  years of age and has not had menses for greater than 1 year will be considered postmenopausal), or 3) not heterosexually active for the duration of the study. The two birth control methods can be either two barrier methods or a barrier method plus a hormonal method to prevent pregnancy. Subjects should start using birth control from study visit 1 throughout the study period up to 120 days after the last dose of study therapy.

The following are considered adequate barrier methods of contraception: diaphragm, condom (by the partner), intrauterine device, sponge, or spermicide. Appropriate hormonal contraceptives will include any registered and marketed contraceptive agent that contains an estrogen and/or a progestational agent (including oral, subcutaneous, intrauterine, or intramuscular agents).

Subjects should be informed that taking the study medication may involve unknown risks to the fetus (unborn baby) if pregnancy were to occur during the study. In order to participate in the study, they must adhere to the contraception requirement (described above) for the duration of the study and during the follow-up period defined in Section 7.3.9 - Reporting of Pregnancy and Lactation to the regulatory agencies and Merck. If there is any question that a subject will not reliably comply with the requirements for contraception, that subject should not be entered into the study.

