#### 1.1.2 Hormone-sensitive breast cancer

More than two-thirds of all advanced breast cancers are dependent on estrogen. Estrogen withdrawal by physical removal of the ovaries or inhibition of their function has been one of the earliest successful interventions against breast cancer; however, this intervention was limited to premenopausal women. The introduction of the SERMs (selective estrogen receptor modulators) has dramatically improved the survival of women with breast cancer, both pre- and post-menopausal. The most prominent SERM is tamoxifen, which until recently has been the gold standard for first-line therapy in women with advanced hormone-sensitive breast cancer. The production of estrogen in postmenopausal women requires an enzyme called aromatase, which can be successfully blocked chemically. The introduction of several aromatase inhibitors (AIs) has added greatly to the arsenal against breast cancer, and they have replaced tamoxifen as first-line therapy in the postmenopausal setting. The most commonly used aromatase inhibitors include letrozole, anastrozole, and exemestane.

However, the AIs are reserved for women who have naturally entered menopause or have their ovarian function suppressed. For premenopausal women or women who are unable to tolerate AIs, tamoxifen remains the gold standard.

The response rate to first-line hormonal therapy, determined from four pivotal randomized Phase III trials, ranges from 20-33%. The response rate to second-line hormonal therapy is considerably less (10-20%), suggesting a clear need for more effective therapy.

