#### 3.3.1 Inclusion Criteria

1. Pre and postmenopausal women or men with stage IV ER+ breast cancer histological or cytological confirmation, 18 years of age or older.

Because no dosing or adverse event data are currently available on the use of pembrolizumab, vorinostat, or tamoxifen in patients <18 years of age, children are excluded from this study but will be eligible for future pediatric trials.

2. >10% expression of PD-1/CTLA-4 dual staining in CD8 cells in tumor or blood or  $\geq 5\%$  expression of PD-1/CTLA-4 dual staining in CD4 in blood (only).
3. Eastern Cooperative Oncology Group (ECOG) Performance Status of  $\leq 1$ .
4. Understand and voluntarily sign an informed consent prior to any study-related assessments or procedures are conducted and are able to adhere to the study visit schedule and other protocol requirements.
5. Consent to paired tumor biopsy
6. Measurable tumor by RECIST criteria
7. Per Good Clinical Practice, any toxicity related to prior therapies that, in the opinion of the investigator, would potentially be worsened with anti-PD1 therapy should be resolved to less than Grade 1
8. Adequate organ function:
  - Absolute neutrophil count (ANC)  $\geq 1.5 \times 10^9/L$
  - Hemoglobin (Hgb)  $\geq 9g/dL$  (may transfuse if clinically indicated)
  - Platelets (plt)  $\geq 100 \times 10^9/L$
  - Potassium within normal range, or correctable with supplements;
  - AST and ALT  $\leq 2.5 \times$  Upper Limit Normal (ULN) or  $\leq 5.0 \times$  ULN if liver tumor is present;
  - Serum total bilirubin  $\leq 1.5 \times$  ULN
  - Serum creatinine  $\leq 1.5 \times$  ULN, or 24-hr clearance  $\geq 60ml/min$ ; and
9. Females of childbearing potential (defined as sexually mature women who):
  - Has not undergone a hysterectomy (the surgical removal of the uterus) or bilateral oophorectomy (the surgical removal of both ovaries) or,
  - Has not been naturally postmenopausal for at least 24 consecutive months (i.e., has had menses at any time during the preceding 24 consecutive months) must have
    - Negative serum pregnancy test within 14 days before starting study treatment in females of childbearing potential (FCBP) and willingness to adhere to acceptable forms of birth control (a physician-approved contraceptive method (oral, injectable, or implantable hormonal contraceptive; tubal ligation; intra-uterine device; barrier contraceptive with spermicide; or vasectomized partner)

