### **4.1.3 Investigational Product: Tamoxifen**

#### Classification

Non-steroidal anti-estrogen

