**Table 5.3 Arm B Regimen Description**

Investigational Product	Premedication; precautions	Dose	Route	Schedule	Cycle Length
Pembrolizumab	No premedications No precautions	200 mg	Intravenous	Day 1, Week 1 Cycles 1+	3 weeks (21 days)
Tamoxifen	No premedications No precautions	20 mg (tablets)	Oral	Daily continuous All cycles	

Tamoxifen may be omitted in Arm B at the PI's discretion

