## **6.6 Prohibited Medications**

Subjects are prohibited from receiving the following therapies during the Screening and Treatment Phase (including retreatment for post-complete response relapse) of this trial:

- Anti-cancer systemic chemotherapy or biological therapy
- Immunotherapy not specified in this protocol
- Chemotherapy not specified in this protocol
- Investigational agents other than Pembrolizumab
- Radiation therapy

- Note: Radiation therapy to a symptomatic solitary lesion or the brain may be allowed after consultation with the study PI and Merck.
- Live vaccines within 30 days prior to the first dose of trial treatment and while participating in the trial. Examples of live vaccines include, but are not limited to, the following: measles, mumps, rubella, chicken pox, yellow fever, rabies, BCG, and typhoid (oral) vaccine. Seasonal influenza vaccines for injection are generally killed virus vaccines and are allowed; however, intranasal influenza vaccines (e.g., Flu-Mist®) are live attenuated vaccines and are not allowed.
- Glucocorticoids for any purpose other than to modulate symptoms from an event of clinical interest of suspected immunologic etiology. The use of physiologic doses of corticosteroids may be approved after consultation with the study PI and Merck.

Subjects who, in the assessment by the investigator, require the use of any of the aforementioned treatments for clinical management should be removed from the trial. Subjects may receive other medications that the investigator deems to be medically necessary.

The Exclusion Criteria describes other medications, which are prohibited in this trial.

There are no prohibited therapies during the Post-Treatment Follow-up Phase.

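### The contraception rules accept estrogen-containing products for premenopausal women with stage IV ER+ breast cancer who are given an anti-estrogen by default

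*Combined protocol and SAP*

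**What the plan says.** The contraception text in Section 6.5.2 asks women who could conceive to use two methods: either two barrier methods, or one barrier and one hormonal method. On the hormonal option it states: "Appropriate hormonal contraceptives will include any registered and marketed contraceptive agent that contains an estrogen and/or a progestational agent". It counts the intrauterine device among the barrier methods.

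Inclusion item 9 (Section 3.3.1) asks females of childbearing potential to use acceptable birth control, which it describes as "a physician-approved contraceptive method (oral, injectable, or implantable hormonal contraceptive", followed by several non-hormonal options. It does not mention estrogen content.

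Item 1 of the same section defines the population as "Pre and postmenopausal women or men with stage IV ER+ breast cancer". Section 4.1.3 classes tamoxifen as "Non-steroidal anti-estrogen", and the Study Calendar (Section 6.1) gives it "20 mg once a day continuously". Tables 5.2 and 5.3 put it in both regimens. The only exception is the note under Table 5.3: "Tamoxifen may be omitted in Arm B at the PI's discretion".

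**The concern.** The two contraception passages agree that hormonal products are acceptable. The difficulty is that both run against the population and the treatment. Section 6.5.2 does more than leave estrogen unmentioned: it names estrogen-containing products as appropriate. A site physician or an outside prescriber who follows the protocol as written could therefore start or continue such a product in a woman with estrogen-receptor-positive metastatic cancer while the trial gives her a drug meant to block estrogen.

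What is at stake is the safety of individual patients, through a rule that gives the wrong answer if followed.

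**Working it through.** No arithmetic applies; the check sets the relevant passages side by side.

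1. **Does the permission reach patients the trial intends to enrol?** Yes. Item 1 admits premenopausal women by name, and item 9 is written for women of childbearing potential.

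2. **Does the protocol give its own reasons to avoid estrogen here?** Yes. Section 1.1.2 says that more than two-thirds of advanced breast cancers depend on estrogen, and adds: "Estrogen withdrawal by physical removal of the ovaries or inhibition of their function has been one of the earliest successful interventions against breast cancer". Section 1.3.1.3 reports preclinical work suggesting that hormonal therapy has to continue when an HDAC inhibitor is given. Tamoxifen is in both regimens by default.

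3. **Does any other rule withdraw the permission?**
   - Exclusion criteria (Section 3.3.2): none names estrogen or hormonal contraception. Exclusion 6 lets the investigator exclude a patient for a therapy that could confound results or where taking part is not in her interest. That is a discretionary judgement about one patient.
   - Item 9: the method must be approved by a physician. This too is case by case, and the physician is told in Section 6.5.2 that estrogen products are appropriate.
   - Section 6.5.1: concomitant drugs are recorded and given at the investigator's discretion; there is no estrogen limit.
   - Section 6.6: the list covers anticancer, immune, investigational and radiation therapy, live vaccines and glucocorticoids. Contraceptives and estrogens are absent.
   - Appendix 3: a drug-by-drug list with no estrogen product and no hormonal contraceptive.

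4. **Would a Section 6.6 entry be the right remedy?** No, for two reasons. That section says that patients judged to require a listed treatment for clinical management should be removed from the trial, which is out of proportion when a woman only needs another method. It also says: "There are no prohibited therapies during the Post-Treatment Follow-up Phase". The duty to use contraception runs on after the last dose (Section 6.5.2 and inclusion item 10), so a listing there would lapse while the permission in Section 6.5.2 still stood.

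5. **Is a hormonal method needed at all?** No. Two barrier methods satisfy Section 6.5.2, and item 9 already lists non-hormonal options. Removing estrogen products leaves every woman a compliant choice.

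**The case against.** The strongest reply is that harm is inferred. No passage says that an estrogen contraceptive defeats tamoxifen at this dose or worsens this disease. Section 1.1.1 even lists estrogen administration among historical endocrine treatments. Section 1.1.3 says that women with hormone-resistant disease gain little from endocrine therapy. No eligibility item requires ovarian suppression, so tamoxifen is already given to women who make their own estrogen. In a single-site trial, physician approval is also a working control.

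Part of this stands: the documents do not measure the harm, and physician approval makes actual use less likely. But none of these passages is offered as a reason to allow estrogen contraception, and the plan keeps tamoxifen despite resistance. Accepting a woman's own estrogen is also a different matter from approving an added source. Discretion to refuse does not correct a sentence that calls the product appropriate.

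Two objections to the remedy stand in full. Men are eligible, and inclusion item 10 puts contraception duties on male participants, so a blanket ban in Section 6.5.2 could reach a male patient's partner who does not have the disease. And, as shown above, Section 6.6 is the wrong place for the rule.

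**Conclusion.** The point holds as a narrow patient-safety error in wording, worth correcting at the next amendment. It rests on the plain text of Section 6.5.2 and item 9, on the absence of any overriding rule, and on the protocol's own account of estrogen dependence and of tamoxifen as an anti-estrogen.

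The number of women affected may be small or zero. The documents give no count of women of childbearing potential. The pilot's median age was 56 with a range of 32 to 81 (Section 1.5), so younger patients do enter this setting, but their sex, menopausal status and contraceptive use are not reported.

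Three stronger readings are tempting and are not supported:

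- *That the 24-week response rate or the comparison between arms is biased.* The documents give neither the frequency of estrogen use nor an effect size, and nothing suggests that use would differ between arms.
- *That the combination adds to clotting risk.* Section 1.2.3 calls thromboembolism tamoxifen's most serious side effect, but the documents give no risk for estrogen contraceptives.
- *That the length of the contraception period measures the harm.* It measures how long a woman must use some method; it says nothing about exposure to estrogen.

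**What to change.** Change the contraception text in Section 6.5.2 and inclusion item 9, for female patients only. Suggested wording: *Female patients must not use a contraceptive that contains an estrogen and should use non-hormonal methods; two barrier methods, of which an intrauterine device may be one, are sufficient. Any estrogen-free hormonal product is a decision for the treating oncologist.* Say expressly that the options for partners of male patients are unchanged.

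Do not add the item to Section 6.6. An Appendix 3 entry limited to female patients is optional; that list already carries entries that apply to one arm only, so a limited entry fits its format.

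Use the concomitant-medication record kept under Section 6.5.1 to find any enrolled woman using such a product and move her to an accepted method. If the consent form, which was not available for review, repeats the permission, it needs the same edit.

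The cost is amendment wording, with no added visits or procedures. The downside is slightly fewer contraceptive choices, and a current user has to switch.
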